8.7.2.2 Secondary/Sensitivity analyses of the primary efficacy endpoint

Several sensitivity analyses will be conducted on the primary efficacy analysis:

- 1) The primary efficacy analysis will be repeated using observed data without imputation. This analysis will be conducted on both the ITT and the PP populations.
- 2) Subjects in the MYL-1601D group who are missing ADA values, and thus a TEAR assessment, will have their TEAR status at Week 24 imputed as positive. No imputation will be done for missing values in the NovoLog® group.
- 3) A tipping point analysis will be implemented following Liublinska and Rubin (2014). See below.

The ADA TEAR rate for each treatment group, and the difference between treatments, for

subjects who are missing data during the treatment period will be summarized for all sensitivity analyses.

The number and percent of subjects with TEAR will be summarized by treatment for each study visit during the treatment period by using similar TEAR definition: ADA negative at baseline become positive at specific visit, and ADA positive at baseline and become 4-fold increase in titer at specific visit.

A by-subject listing will be provided for observed and derived variables.

8.7.2.3 Tipping point analysis

A tipping point analysis will be used to estimate the point at which the equivalence boundary is crossed and the results fail to reject non-equivalence; that is, where

$$|\hat{p}_M - \hat{p}_N| \geq \delta, \delta > 0$$

The tipping point analysis will consider all possible counts of TEAR positive subjects that could result if TEAR status could be observed for each missing value. This will range from all missing values being imputed as positive to all missing values imputed as negative. Following Liublinska and Rubin (2014), a graphical display (heat map) is used to indicate the tipping point analysis results for each combination of imputed missing values. The risk difference in TEAR rate across the treatment arms is presented for each combination in the heat map. The graph will display the sensitivity across the range of missing values as a color gradient from most favorable for the test treatment arm to the most favorable for the reference treatment.

In addition, the TEAR rate at each scheduled visit (visitwise TEAR [vTEAR]) will be summarized at each scheduled visit by using the following criteria: Subjects who are ADA negative at baseline and become positive at a specific visit (Treatment Induced TEAR), and subjects who are ADA positive at baseline and obtain a 4-fold increase in titer at a specific visit (Treatment Boosted TEAR), will each be counted as TEAR positive at the specified visit.

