8.7.2.1 Primary efficacy analysis

The primary efficacy analysis will be a test of equivalence for the MYL-1601D and NovoLog® groups in the TEAR rate at Week 24. The null hypothesis is non-equivalence, expressed by

$$H_0: |p_M - p_N| \geq \delta, \delta > 0$$

where p_M and p_N are the (true) proportions of subjects with TEAR in the MYL-1601D and NovoLog[®] groups, respectively, and δ is the equivalence margin. The null will be rejected in favor of equivalence if the 90% confidence interval of the treatment difference is within the range $(-\delta, \delta)$. The confidence interval as defined by Chow and Shao (2002) is constructed as

$$CI_{2\alpha} = [\hat{p}_M - \hat{p}_N - t_\alpha \hat{\sigma}, \hat{p}_M - \hat{p}_N + t_\alpha \hat{\sigma}]$$

where \hat{p}_j is the estimate of the TEAR rate p_j in each treatment group, $j \in \{M, N\}$, $\hat{\sigma}$ is the sample estimate of the standard error of the mean, and t_α the 0.05 quantile of the t distribution with $(N - 2)$ degrees of freedom with N being the pooled number of subjects in the analysis. That is, H_0 will be rejected if neither $-\delta$ nor δ is contained within the 90% confidence interval.

To minimize any bias due to missing data, the primary efficacy analysis will use multiple imputation to fill in missing ADA values. Multiple imputation (MI) will be applied to two measured variables: ADA binary response (positive/negative) and ADA continuous titer values. Multiple imputation will be done for each variable separately, then the two sets of imputed datasets will be merged in order to generate the imputed TEAR status. For subjects who are ADA negative at baseline, post-baseline missing values will be imputed using the binary response values obtained from logistic regression MI. Missing post-baseline values for subjects who are ADA positive at baseline will be derived from the continuous MI model. The primary efficacy analysis is based on the Week 24 (Visit 15) value. Subjects who discontinue treatment prematurely will be classified based on whether ADA values were obtained for the visits after treatment discontinuation (retrieved dropouts) or not.

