10.2 Tipping Point Analysis

The tipping point analysis will create a type of figure called a heat map. It will not impute data at the subject level, but rather will be based on the observed total counts of TEAR status and number of missing values per group.

The steps are summarised below:

For purposes of the code below, set

```
Nm = Total # of subjects randomized to MYL-1601D group
Nn = Total # of subjects randomized to Novolog group
Mm = # of subjects missing TEAR status in MYL-1601D
group
Mn = # of subjects missing TEAR status in Novolog group
TEARm = # of subjects in MYL-1601D group who are TEAR
positive
TEARn = # of subjects in Novolog group who are TEAR
positive
```

Then run code similar to the following. The code below assumes that the above variables have been created as global variables.

```
%macro heat;

data heatmap;
do i = 0 to &mn;
  do j = 0 to &mm;
    y = &tearn + i;
    x = &tearm + j;
    pn = y/&nn;
    pm = x/&nm;
    riskdiff = pm - pn;
    margin = (quantile('NORMAL',0.95) +
    quantile('NORMAL',0.90))*
    sqrt(2*pn*(1-pn)/&nn);
    output;
  end;
end;
run;

%do i = 0 %to &mn;
  %do j = 0 %to &mm;

    data imputed;
    length group $8;
    group="NOVOLOG";
    status=1;
    count=%eval(&tearn+&i);
    output;
    status=0;
    count=%eval(&nn - (&tearn+&i));
    output;
```

```

group="MYL-1601D";
status=1;
count=%eval(&tearm+&j);
output;
status=0;
count=%eval(&nm - (&tearm+&j));
output;
run;

ods exclude all;
proc freq data=imputed;
table group * status / riskdiff (cl=WALD column=2)
alpha=0.1;
weight count;
ods output riskdiffcol2=rdiff1;
run;
ods exclude none;
data ci;
set rdiff1 (where=(row="Difference"));
y = &tearn + &i;
x = &tearm + &j;
run;

data heatmap;
merge heatmap
ci (keep=x y risk ase lowercl uppercl)
;
by x y;
length color $8 digits $16 a1-a6 asterisk $1;
if -0.0000001 <riskdiff < 0.0000001 then do;
red=255;
green=255;
blue=255;
end;
else if riskdiff > 0 then do;
if riskdiff >= 0.16 then do;
red = round(484 - (1435*riskdiff));
green = 0;
blue = 0;
end;
else do;
red = 254;
green = round(255/(1+exp(-32.96*(0.1149-
abs(riskdiff)))));
blue = round(255/(1+exp(-21.58*(0.0793-
abs(riskdiff)))));

```

```

        end;
    else if . < riskdiff < 0 then do;
        red = round(255/ (1+exp(-18.51*(0.1108-
abs(riskdiff)))));
        green = round(255/ (1+exp(-27.85*(0.1699-
abs(riskdiff)))));
        blue = round(255/ (1+exp(-20.10*(0.1024-
abs(riskdiff)))));
    end;

    digits = "0123456789ABCDEF";

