    n1 = floor(red/16);
    n2 = red - (n1*16);
    a1 = substr(digits,n1+1,1);
    a2 = substr(digits,n2+1,1);
    n3 = floor(green/16);
    n4 = green - (n3*16);
    a3 = substr(digits,n3+1,1);
    a4 = substr(digits,n4+1,1);
    n5 = floor(blue/16);
    n6 = blue - (n5*16);
    a5 = substr(digits,n5+1,1);
    a6 = substr(digits,n6+1,1);
    color = compress("CX"||a1||a2||a3||a4||a5||a6);

    if (lowercl < (margin) < uppercl) and
        (lowercl < (-margin) < uppercl) then asterisk=" ";
    else asterisk="*";

    run;

    %end;
%end;
%mend heat;

%heat;
```

This code will create a dataset called HEATMAP that contains the X and Y variables, risk difference, and color to use for the plot. There will be (Mm+1) values on the x-axis and (Mn+1) values on the y-axis. These will be the number of subjects with TEAR=1 in the MYL-1601D (x-axis) and Novolog (y-axis) groups, respectively, based on all possible counts that could be observed if the missing TEAR values were known. The HEATMAP dataset provides these counts as variables x and y for each row.

The heat map figure will consist of a grid with dimensions (Mm+1) × (Mn+1). The x-axis

will be labeled with the range of values of the variable x in the HEATMAP dataset, and the y-axis will be labeled with the range of y values. Each row in the HEATMAP dataset corresponds to one rectangle on the grid. Within that one rectangle should be printed the value of the variable RISKDIFF. If the value of RISKDIFF lies outside the margin, then an asterisk should be appended to the numeric value of RISKDIFF. A variable ASTERISK has been created in the sample code for this purpose.

The rectangle itself should be filled with color, which will be generated based on the value of RISKDIFF. Shades of red color will indicate that the TEAR rate is higher in the MYL-1601D group, while green shades will indicate a higher TEAR rate in the Novolog group. The color intensity will increase as the magnitude of RISKDIFF becomes more extreme. Colors will be programmatically assigned and will be captured in hexadecimal format in the variable COLOR in the HEATMAP dataset. This hexadecimal value can be supplied to the SAS graphics procedure.

The heat map will display the number of TEAR events in the MYL-1601D group in descending order on the x-axis and number of TEAR events in the Novolog group in descending order on the y-axis. An example is provided in the figure shells.

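### The SAP's tipping-point rules for TEAR conflict with each other, and none matches the primary decision that the whole 90% CI must lie within the margin

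*SAP*

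**What the plan says.** The SAP describes the equivalence decision or its tipping point in four places that bear on this.

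- **Primary rule, SAP 8.7.2.1.** "The null will be rejected in favor of equivalence if the 90% confidence interval of the treatment difference is within the range" (−δ, δ). Protocol 7.2.2 and 7.2.3 say the same.
- **Tipping definition, SAP 8.7.2.3.** The analysis is to estimate "the point at which the equivalence boundary is crossed and the results fail to reject non-equivalence; that is, where" the absolute difference of the two estimated rates is at least δ. The formula carries hats and no standard error.
- **Figure text, SAP Appendix 10.2.** "If the value of RISKDIFF lies outside the margin, then an asterisk should be appended to the numeric value of RISKDIFF". RISKDIFF is the plain difference of the two proportions in that cell.
- **Example code, SAP Appendix 10.2.** The code computes a 90% Wald CI for each cell and leaves the asterisk blank under two joint conditions: "if (lowercl < (margin) < uppercl) and" the matching line "lowercl < (-margin) < uppercl) then asterisk" is set to blank. Every other cell is starred.

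Near the end of SAP 8.7.2.1, another sentence declares equivalence when the margin falls inside the CI. That reverses the rule given earlier in the same section. Protocol 7.2.4 names the tipping-point method but gives no threshold.

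**The concern.** A tipping-point analysis asks how adverse the missing outcomes must be before the primary conclusion changes, so it has to apply the primary decision rule cell by cell. Failing to reject non-equivalence and having an observed difference of at least δ are different events. The first happens as soon as one limit of the 90% CI reaches the margin, while the point estimate is still well inside it.

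Under the written rule, there is a band of cells in which equivalence would not have been declared but which the map shows as not tipped. Under the printed code, the map shows everything as tipped. This is the plan's only analysis that covers every combination of missing TEAR outcomes in both arms, so a wrong flag would misinform whoever uses it to judge how far the result depends on missing ADA data.

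**Working it through.** **Inputs.** 250 per arm (SAP 5). Margin from SAP 8.7.2.1 and the 10.2 code, which starts "margin = (quantile('NORMAL',0.95" and adds the 0.90 normal quantile: δ = (1.645 + 1.282) × √(2p(1−p)/n) = 2.926 × √(2p(1−p)/250), where p is the NovoLog rate. 90% Wald limits: difference ± 1.645 × SE, with SE = √(pM(1−pM)/250 + pN(1−pN)/250).

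**The plan's own figures reproduce.** At p = 0.20, δ = 2.926 × √(0.32/250) = 2.926 × 0.03578 = 10.47%; Table 2 gives 10.5%. All 12 rows agree within 0.05 percentage points. Power at zero true difference, 2Φ(δ/SE − 1.645) − 1, is 79.5% to 80.6% with the tabulated margins.

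**One rate in full (NovoLog 50/250, MYL-1601D starting at 50/250).** Turn missing MYL-1601D subjects positive one at a time, with the NovoLog count fixed.

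- 10 extra: difference 4.0%, SE 3.70%, upper limit 4.0 + 6.09 = 10.09%. This is below 10.47%, so still equivalent.
- 11 extra: difference 4.4%, SE 3.71%, upper limit 10.51%. This is above 10.47%, so equivalence is lost.
- 26 extra: difference 10.4%. This is below 10.47%, so the written rule has not tipped.
- 27 extra: difference 10.8%, 90% CI 4.45% to 17.15%. The written rule tips here.

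From 11 to 26 extra positives (16 counts), the primary test has failed and the written rule shows no tip.

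**Other rates, starting from equality.**

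| NovoLog rate | δ | CI rule tips at | Written rule tips at | Ratio |
|---|---|---|---|---|
| 10% | 7.85% | 8 | 20 | 2.50 |
| 20% | 10.47% | 11 | 27 | 2.45 |
| 30% | 11.99% | 13 | 30 | 2.31 |
| 40% | 12.82% | 14 | 33 | 2.36 |
| 50% | 13.09% | 15 | 33 | 2.20 |

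Over all 12 Table 2 rates the ratio is 2.2 to 2.5. With a constant SE it would be 2.926/(2.926 − 1.645) = 2.926/1.282 = 2.28.

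**Dependence on the observed difference (20% rate).** The ratio is 3.0 if MYL-1601D starts 1.2 points higher (24/8), 2.0 if 2 points lower (32/16), 1.84 if 3.2 points lower (35/19) and 1.76 if 4 points lower (37/21). The absolute gap stays at 16 counts. From equality it is 8 to 19 counts across Table 2.

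**The printed code.** A blank needs both −δ and +δ inside the CI, so the CI must be wider than 2δ, about 2 × 2.926 = 5.85 SE. At similar rates the 90% CI is only 2 × 1.645 = 3.29 SE wide. Checking all 251 × 251 = 63,001 count pairs at 250 per arm gives 4 blank cells. In all four the NovoLog rate is 0% or 100%, so the margin is zero. Every cell with a non-zero margin is starred.

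**The case against.** The best defence is that the CI-based intent is already visible. The words in 8.7.2.3 speak of failing to reject non-equivalence, 8.7.2.1 ties rejection to the 90% CI, and the code computes CI limits for each cell. On this view the displayed formula is the null hypothesis with hats added by mistake. That is plausible, but it does not settle the matter: the figure text separately states the point-estimate rule, and the code that uses the CI is inverted.

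A reader might infer that the finished map would make the result look more than twice as robust as it is. The documents do not support that as a flat statement, for three reasons.

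- The figure text points to the ASTERISK variable in the code for the flag. Run as printed, that code would show no robustness at all. The code is offered only as an example, so neither display is certain.
- The ratio exceeds two only when the observed rates are close or MYL-1601D is higher. It is below two when MYL-1601D starts sufficiently lower.
- The number of missing TEAR statuses is not given, and Protocol 7.1 allows for no attrition. From equality, if fewer than about 6 to 15 MYL-1601D statuses are missing (depending on the rate), neither rule tips in that direction.

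It is also fair to say that another sensitivity analysis (Protocol 7.2.4; SAP 8.7.2.2, item 2) sets every missing MYL-1601D subject to TEAR positive, and that the protocol asks for a 90% Wald CI there. That covers one adverse scenario properly, but it does not locate the tipping boundary.

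**Conclusion.** The point stands as an internal contradiction that leaves the tipping-point analysis without a correct rule. The text of 8.7.2.3 and 10.2 tests the point estimate, the code of 10.2 tests the CI the wrong way round, and neither reproduces the decision in 8.7.2.1.

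If the text is followed, the error always runs toward overstated robustness: 2.2- to 2.5-fold in extra MYL-1601D positives from equal observed rates, and about 1.8-fold at a 20% NovoLog rate when MYL-1601D starts 3.2 points lower. If the code is followed, the map is uninformative in the opposite direction.

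These sizes assume 250 analysed per arm, a fixed NovoLog count and the z-based Wald limits of the SAP code. Whether any cell is actually mislabelled depends on how many TEAR statuses are missing, which the documents do not state. It would go too far to infer that the primary conclusion is at risk: the primary estimate, interval, margin and decision do not use this display.

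**What to change.** 1. In SAP 8.7.2.3, replace the formula with: a cell is tipped when its 90% Wald CI is not wholly inside (−δ, δ), that is, lower limit ≤ −δ or upper limit ≥ δ, with δ computed from that cell's NovoLog rate.
2. In the Appendix 10.2 figure text, tie the asterisk to the same condition. Keep RISKDIFF as the printed value and the basis for the colour only.
3. In the Appendix 10.2 code, replace the flag with: `if lowercl <= -margin or uppercl >= margin then asterisk="*"; else asterisk=" ";`.
4. In SAP 8.7.2.1, correct the later sentence so that equivalence is declared when the CI lies within the margins, not when the margin lies within the CI.

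The cost is a few sentences and one code statement. The limits and the margin are already held in the HEATMAP dataset, and no new data are needed. Compared with the written rule the map becomes less favourable; compared with the printed code it becomes more favourable. The change should be made before the treatment codes are released.

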8.7.3 Secondary endpoints

The following efficacy measures (both actual and change values) will be summarized at baseline and each scheduled visit.

- Change in HbA1c from baseline.
- Change in fasting plasma glucose from baseline.
- Change in prandial, basal insulin and total daily insulin dose per unit body weight (U/kg) from baseline.
- Change in 7-point self-monitored blood glucose (SMBG) profile from baseline.

A mixed model for repeated measures (MMRM) will be performed for continuous variables without imputing missing values. The MMRM model will include the fixed, categorical

effects of treatment group assignment, visit, treatment group-by-visit interaction, basal insulin dose time (AM/PM), and investigative site, as well as the baseline value as a continuous covariate.

The MMRM model results will be presented along with Least Squares (LS) means for the difference between the MYL1601-D and NovoLog[®] groups, standard errors, and two-sided 95% CIs for the difference between treatment groups. Contrasts of LS means at each scheduled visit will be used to evaluate all pairwise treatment comparisons, and 95% confidence intervals for treatment differences in LS means will be computed for each visit. The interaction of time points and treatment groups will also be presented. An unstructured covariance matrix will be assumed for within-subject error. The denominator degrees of freedom will be calculated according to the Kenward-Roger method.

In case of non-convergence of the above model using an unstructured covariance matrix, the following variance structures will be tested, and based on Akaike's information criteria the best fitting model will be chosen. The variance structures that will be considered for the within-subject variation in case of non-convergence are in this order: Heterogeneous Toeplitz, Toeplitz, and Compound Symmetry.

If convergence is still not obtained, the model may be revised to remove investigative site from the list of covariates.

All of the above analyses will be performed on the ITT set.

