7.3 Secondary Endpoints

The following efficacy measures (both actual and change values) will be summarized at baseline and scheduled visit. A mixed model repeated measures (MMRM)-effects model will be performed for continuous variables without imputing missing values. The MMRM model will include the fixed, categorical effect of treatment group assignment, visit, treatment group-by-visit interaction and the other fixed effect terms Investigator, basal insulin dose time, and baseline value as covariates. Contrasts of LS mean at each scheduled visit will be used to evaluate all pairwise treatment comparisons, and 95% confidence intervals for treatment differences in LS means will be computed for each visit.

- Change in HbA1c from baseline.
- Change in fasting plasma glucose from baseline.
- Change in prandial, basal insulin and total daily insulin dose per unit body weight (U/kg) from baseline.
- Change in 7-point SMBG profile from baseline.

All above analyses will be performed on ITT set.

A sensitivity analysis for HbA1c will be performed using multiple imputation to impute missing values with non-missing subjects within same treatment group using pattern mixture model with the complete-case missing values (CCMV) method ([Little 1993](#)). After imputation, treatment difference, 95% CI, and p-values will be generated using same MMRM model as above.

The following safety measures (both actual and change values) will be summarized at baseline and scheduled visit. Similar MMRM model as efficacy analysis will be conducted for hypoglycemia rate. For antibody continuous variables, the MMRM model will include the fixed, categorical effect of treatment group assignment, visit, treatment group-by-visit interaction and the other fixed effect terms Investigator and baseline value as covariates. Contrasts of LS mean at each scheduled visit will be used to evaluate all pairwise treatment

comparisons, and 95% confidence intervals for treatment differences in LS means will be computed for each visit. For categorical data analyses, Fisher's exact test or Chi-squared test will be used.

The following analyses will also be performed and will form part of the totality of evidence to compare clinical efficacy and safety of two treatment groups:

- Incidence of ADA response and positive cross-reactive ADA; and incidence of positive NABs.

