4.2 Secondary efficacy endpoint(s)

The secondary endpoint points are change from baseline to week 24 for the ITT population.

- Change in HbA1c from baseline
- Change in fasting plasma glucose from baseline
- Change in prandial, basal and total daily insulin dose per unit body weight (U/kg) from baseline
- Change in 7-point SMBG profile from baseline

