8.8.5 Immunogenicity assessments

For antibody continuous variables, the MMRM model will include the fixed, categorical effect of treatment group assignment, visit, treatment group-by-visit interaction and the other fixed effect terms investigator and baseline value as covariates. Contrasts of LS mean at each scheduled visit will be used to evaluate all pairwise treatment comparisons, and 95% confidence intervals for treatment differences in LS means will be computed for each visit. For categorical data analyses, Fisher's exact test or Chi-squared test will be used.

The following analyses will also be performed.

- Incidence of ADA by visit, incidence of positive cross-reactive ADA by ADA status and by visit, and incidence of NABs.
- Analysis of potential impact of TEAR status on efficacy and safety parameters such as HbA1c, glucose control FPG, insulin dose, hypoglycemic rate, and Incidence of any injection site allergic reactions and hypersensitivity.

To explore the potential ADA impact on the subjects' glucose control, scatter plots of maximum TEAR values with HbA1c, FPG and total daily insulin dose will be displayed by treatment. In addition, the following analyses will be performed:

- TEAR effect on Efficacy will be assessed using the following:
 - 1) HbA1c and total insulin dose values by TEAR status and treatment group.
 - 2) A summary of subjects who experience meet vTEAR criteria, an increase in A1c of at least 0.2% from baseline, and an increase in the total dose from baseline at a protocol scheduled visit (where immunogenicity, A1c and dose all measured). This summary will be provided by visit, by treatment group, and overall.
- TEAR effect on Safety will be assessed using the following:

- 1) Hypoglycemic rate by treatment group and TEAR status.
- 2) Incidence of injection site allergic reactions and incidence of hypersensitivity in TEAR positive subjects.
- 3) Incidence of positive NAb by TEAR status and treatment group.

All the above analyses will be performed on the safety set.

The NAb actual assay results will not be available at the time of database lock (EDC database lock) for the analysis. However, the treatment will remain blinded during the laboratory assay. These data will be sent later from assay lab and statistical analysis will be performed according to pre-specified method in this SAP.

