proc mi data=outdata1 seed=24637883 nimpute=30  
out=outdata2;  
by treatment;  
monotone reg(hb11 hb15 / details);  
mnar model (hb11 hb15 / modelobs=ccmv(k=1));  
var hb0 hb11 hb15;  
run;
```

Step 4.

Reverse the process from Step 1, creating one record per subject visit, retaining the imputation number on each record.

Step 5.

Use code similar to what was used to analyze the primary efficacy endpoint, but run the code by `_imputation_`. For example,

```
/** step 5: Analyze the imputed datasets */  
proc sort data=imputed;  
by _imputation_ subjid avisitn;  
run;  
  
proc mixed data=imputed;  
by _imputation_;
```

```
class trt avisitn dosetime site;
model chg = trt avisitn dosetime site trt*avisitn base /
ddfm=kr s;
repeated avisitn / type=un;
lsmeans trt*avisitn / diff cl;
ods output ConvergenceStatus=converge;
ods output diffs=trtdiff;
run;
```

Convergence status is assessed by the condition that:

```
if pdg=1 and pdh=1 and status=0
```

in the dataset converge above, then model has converged. In the above code, if the model does not converge, replace the type=un option by each of the following: type=toeph, type=toep, and type=cs. You will also need to replace ddfm=kr with ddfm=bw. Choose the best fit model by checking the AIC and selecting the model with the lowest one. Please contact the statistician if this step is necessary.

Step 6.

Combine the 30 estimated statistics into one using PROC MIANALYZE.

```
data trtdiff;
set trtdiff (where=(avisitn=_avisitn));
run;

proc sort data=trtdiff;
by avisitn _imputation_;
run;

[figure not shown]
proc mianalyze data=trtdiff;
by avisitn;
modeleffects estimate ;
stderr stderr;
ods output parameterestimates=parms;
run;

proc print data=parms;
var avisitn estimate stderr lclmean uclmean probt;
run;
```

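### The repeated-measures model uses one pooled baseline slope for every visit; if that slope changes over time, the Week 24 intervals are somewhat wider than they need to be

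*SAP*

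**What the plan says.** The model is described in three places, which agree.

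- SAP 8.7.3 lists treatment, visit, treatment-by-visit, and then "basal insulin dose time (AM/PM), and investigative site, as well as the baseline value as a continuous covariate".
- Protocol 7.3 has the same structure: "treatment group-by-visit interaction and the other fixed effect terms Investigator, basal insulin dose time, and baseline value as covariates".
- The only MMRM code, in SAP Appendix 10.1.4 (Step 5, the HbA1c sensitivity analysis), reads "model chg = trt avisitn dosetime site trt*avisitn base". It has no base*avisitn term.

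The antibody model in SAP 8.8.5 drops dose time but treats baseline the same way: "the other fixed effect terms investigator and baseline value as covariates".

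On the covariance, SAP 8.7.3 says: "An unstructured covariance matrix will be assumed for within-subject error". On the output, "95% confidence intervals for treatment differences in LS means will be computed for each visit". The target time is set in SAP 4.2: "The secondary endpoint points are change from baseline to week 24 for the ITT population".

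From SAP 8.7.3.1 to 8.7.3.4, the modelled post-baseline visits are Weeks 12 and 24 for HbA1c, six visits (Weeks 4 to 24) for FPG, and seven visits (Weeks 2 to 24) for insulin dose and SMBG.

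**The concern.** The treatment effect may differ by visit and the residual covariance is free, but the relation to baseline is held constant from the first visit to the last. An unstructured covariance does not relax this: it frees the residuals, not the regression on baseline.

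The pooled slope is a weighted average of the visit-specific slopes. When early visits are more tightly tied to baseline, they carry most of the weight, while the contrast of interest is at Week 24, furthest from baseline. If the Week 24 slope is lower than the pooled one, the chance baseline difference between arms is multiplied by the wrong coefficient at that visit, and the leftover is extra noise.

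The stake is modest but not nil. Both documents name HbA1c, FPG and insulin dose in the totality of evidence used to interpret the TEAR result, so their intervals should use the collected baseline fully.

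**Working it through.** **The plan's own figures.** The documents give no SD, correlation, power or interval width for any continuous secondary endpoint. The only design figures belong to the TEAR endpoint, and they reproduce. With margin = (1.645 + 1.282) × √(2p(1−p)/250), p = 5% gives 2.926 × 0.01949 = 5.70%, and p = 50% gives 2.926 × 0.04472 = 13.09%. Protocol Table 5 shows 5.7% and 13.1%. Nothing there involves the MMRM.

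**Formula.** Let b_t be the baseline slope at visit t and S the covariance of the post-baseline values given baseline, with all variances scaled to 1. The common-slope model converges to

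b_c = (1′S⁻¹b) / (1′S⁻¹1),

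and the ratio of the Week 24 standard error (planned model over a model with baseline-by-visit) is

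√(1 + (b_c − b_24)² / S_24).

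Working on change rather than value shifts every slope by −1 and leaves the ratio unchanged. **All correlations below are assumptions**; site and dose time are ignored.

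**HbA1c, one case in full.** Take correlations of 0.80 (baseline with Week 12), 0.60 (baseline with Week 24) and 0.75 (Week 12 with Week 24).

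- S_12 = 1 − 0.64 = 0.36; S_24 = 1 − 0.36 = 0.64; covariance = 0.75 − 0.48 = 0.27.
- Weights are proportional to 0.64 − 0.27 = 0.37 (Week 12) and 0.36 − 0.27 = 0.09 (Week 24), that is 0.804 and 0.196.
- b_c = 0.804 × 0.80 + 0.196 × 0.60 = 0.761, against b_24 = 0.60.
- Ratio = √(1 + 0.161²/0.64) = 1.020.

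| Assumed HbA1c correlations (base–W12, base–W24, W12–W24) | SE ratio at Week 24 |
|---|---|
| 0.75, 0.75, 0.80 | 1.000 |
| 0.75, 0.65, 0.80 | 1.004 |
| 0.70, 0.50, 0.80 | 1.018 |
| 0.80, 0.60, 0.75 | 1.020 |
| 0.85, 0.60, 0.75 | 1.040 |

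With an assumed SD of 0.9 and 250 per arm, the half-width in the second row is 1.96 × 0.9 × √(2 × 0.5775/250) = 0.120 points, and it stays at 0.120 under the planned model. In the fourth row it goes from 0.126 to 0.129.

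**FPG, dose and SMBG.** Assume correlation a·exp(−k × weeks apart).

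| a, k per week | FPG (6 visits) | Dose/SMBG (7 visits) |
|---|---|---|
| 0.5, 0 | 1.000 | 1.000 |
| 0.7, 0.01 | 1.004 | 1.005 |
| 0.8, 0.02 | 1.018 | 1.025 |
| 0.9, 0.02 | 1.031 | 1.044 |
| 0.95, 0.02 | 1.043 | 1.059 |

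Check on dose at a = 0.8, k = 0.02: b_24 = 0.8 × e^(−0.48) = 0.495 and b_c = 0.692, so √(1 + 0.197²/0.755) = 1.025. The largest entry, 1.059, is a variance 1.059² = 1.12 times as large. These ranges are not bounds: with a = 0.95, k = 0.03, the dose slope falls to 0.462 at Week 24 against b_c = 0.829, giving √(1 + 0.367²/0.787) = 1.082. In the same family with k up to 0.02, HbA1c does not exceed about 1.010.

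**Simulation.** An HbA1c-like trial (250 per arm, SD 0.9, 1,500 runs per setting, unstructured covariance) used the first four rows of the HbA1c table.

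- Complete data or 10% random dropout: bias of the common-slope model was at most 0.001 points and coverage was 94.7% to 95.6%.
- Dropout driven by baseline in opposite directions in the two arms: with a slope gap of 0.1, bias was 0.016 and coverage 95.0%; with a gap of 0.2, bias was 0.036 to 0.038 and coverage 91.0% to 91.5%. The interaction model stayed at 0.002 or less, with coverage near 95%.
- Equal slopes with that same dropout: the common-slope SE was slightly smaller (ratio 0.997). That is the price of the extra term.

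**The case against.** The strongest reply is that this is not an error. Protocol, SAP and code agree, the model is fully prespecified, and parallel baseline slopes are a legitimate choice. That stands.

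The premise is also not shown. Decay with time is a property of correlation, whereas the model fixes the slope, which is correlation times the SD ratio. If change accumulates in independent increments, variance grows, correlation with baseline falls, and the slope stays constant. The pooled slope is then right and the loss is zero. The equal-variance assumption in the calculations excludes this case. That stands too, and it is why the consequence must be stated conditionally.

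For dose in particular, the documents point towards stability: a stable regimen before screening, titration in the run-in, and adjustment kept to a minimum afterwards (Protocol 2.2.1 and 5.1.1). Against that, adjustment is permitted, and Week 12 HbA1c can lead to a change of treatment at Week 16 (Protocol 5.7), so a falling slope cannot be ruled out. The seven-visit dose model is itself less settled than it looks, because SAP 8.7.3.3 describes averages over the treatment period while SAP 8.7.3 asks for contrasts at each visit.

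Two stronger readings are tempting. A reader might infer that the Week 24 contrast is biased or systematically over-corrected. It is not: under randomization the wrong coefficient multiplies a chance imbalance that averages to zero, and simulated coverage was nominal. A reader might also turn an assumed dose case (slopes of 0.88 falling to 0.56, variance 9% higher) into a loss of about 41 of 500 subjects. The documents supply none of those slopes, so that figure describes the assumption and not this trial.

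**Conclusion.** The point holds as a conditional matter of efficiency and robustness. One pooled baseline slope adjusts the Week 24 contrast for every continuous secondary endpoint. If the slope falls over visits, the contrast stays unbiased and its interval valid under randomization with complete data or data missing completely at random, but the interval is wider than necessary.

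Over the settings examined, with correlations decaying and variances equal, the widening is about 0% to 6% for dose and SMBG and 0% to 4% for FPG. For HbA1c it is usually under 1%, about 2% with a slope gap of 0.2 and 4% in the most extreme case. Faster decay would give more; equal slopes give none.

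The added weakness under dropout that depends on baseline differently by arm is a stress case and not a prediction. It deserves mention because sites are unblinded and this MMRM imputes nothing. No margin or success rule is attached to these endpoints, and the TEAR analysis does not use the model, so no prespecified decision turns on it. It is a cheap improvement.

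**What to change.** Add a baseline-by-visit interaction to the MMRM in SAP 8.7.3 and Protocol 7.3, and add base*avisitn to the MODEL statement in SAP Appendix 10.1.4. For consistency, carry it to the other multi-visit models: antibody variables (SAP 8.8 and 8.8.5) and vital signs (SAP 8.9.2, Protocol 7.5.1). Hematology, chemistry and lipids are scheduled after baseline only at Week 24, so the term would do nothing there.

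Protocol section 7 lets the SAP modify the planned analyses and asks for an amendment only for major changes to the primary endpoint or its analysis. A SAP revision before unblinding would therefore suffice, with Protocol 7.3 aligned when next amended.

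The cost is one parameter per visit after the first: one for HbA1c, five for FPG, and six for the endpoints with seven visits, with about 500 subjects. If the slopes are equal, the loss of precision is negligible (about 0.3% of the SE in the least favourable simulated setting).
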